3.2.7.1 Window Period for Screening Laboratory Tests

There is no window for screening laboratory evaluations. These must be collected on Study Day 1. Because of the necessity for prompt anti-rabies care the results may be known and eligibility confirmed after study entry and randomization. This means that some subjects may be found to be ineligible for the study or the per protocol population after randomization.

3.2.8 Per-protocol Adjudication Board (exclusion from the per-protocol population)

Since all inclusion/exclusion criteria are not able to be known at the time of study randomization the per-protocol status of some randomized subjects may need to be changed based on review of blinded screening information that becomes available at a later time. The Sponsor will create the Per-protocol Adjudication Board whose duty will be to review screening data, management information and initial determination of eligibility for the per-protocol population. The Per-protocol Adjudication Board will review blinded data and will not be able to unblind subjects or data. Based on inclusion/exclusion criteria, the protocol deviation and the impact of the deviation on protocol data, the Per-protocol Adjudication Board may exclude randomized subjects from the per-protocol population. Its judgments will be forwarded to the DSMB and the study enrollment center for the adjustment of randomization to maintain stratification and distribution of cases at the different sites. The subjects excluded from the per-protocol population will continue on the study in the “as-treated” population unless they withdraw consent. The Sponsor will maintain a roster of its actions and the reasoning behind them.

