2.6.2 LRG General Enrollment and NRG Randomization

Subjects in the general enrollment of LRG and NRG will be randomized on a 1:1 basis within each group to treatment with SYN023 or HRIG. Subjects will be allocated to treatment sites to approximate the ratio in Table 2.3-1. Within NRG enrollment subjects with head or neck bites or bites to genitalia will be stratified on a 1:1 basis into SYN023 or HRIG treatment groups.

Study sites wishing to randomize a subject will contact the study randomization center either telephonically or by electronic means. The study center will determine the randomization allocation and return the randomization assignment in written communication to the study site.

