2.7 Non-Replacement of Randomized Patients

Subjects will not be replaced after randomization. They may be excluded from the per-protocol population

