2.8 Adjustments to Randomization

Allocation of randomization among sites will be adjusted to accommodate stratification of head, neck or genitalia bites or site enrollment imbalances.

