3.2.6 Major Protocol Deviations and Eligibility for the Per-protocol Population

Continuation in the per-protocol population depends on the absence of uncorrectable major protocol deviations. Major deviations are those that would degrade the fidelity of the data from the protocol. Protocol deviations requiring removal from the per-protocol population include but are not limited to those listed below.

- Defective informed consent
- Received the incorrect Study Drug
- Received the incorrect dose ($\pm 20\%$) of Study Drug
- Failed to complete the scheduled rabies vaccinations through Study Day 29
- Are discovered to lack adequate prophylactic treatment of all exposure sites
- Are discovered to be injured by animal other than those listed
- Are discovered to have an interval > 54 hours from rabies exposure to the start of prophylaxis
- Are discovered to have RVNA ≥ 0.1 IU in serum obtained at Study Day 1
- Receives prohibited treatment during the trial
- Are found not to have a modified WHO Category 3 exposure (Table 2.2-1, Section 3.9.4)
- Are discovered to have or have developed HIV infection or other immunodeficiency state.
- Second high risk animal bite or contact requiring PEP

Subjects who are discovered to not have satisfied any criteria for the per-protocol population may be excluded from that population (Section 3.2.8). These deviations may become known at different intervals from randomization. Likely intervals for discovery of these deviations are listed in Table 3.2.6-1 based on the occurrence of site review, monitoring visits and vaccination schedules.

Table 3.2.6-1 Intervals for Per-protocol Exclusions (approximate)

Major Protocol Deviation	Rationale	Likely Interval Days
Defective consent	Data without effective consent cannot be used	43
Diagnosis of HIV after enrollment	New HIV may affect PEP response	365
Received incorrect study drug	Mixes SYN023 and HIRG results	43
Incorrect dose ($\pm 20\%$) of Study Drug	Arbitrary but reasonable dose margin. Used for biosimilars.	43
> 54 hr from rabies exposure to the Study Drug	Early PEP initiation is important Should be discovered early from wound state and investigation	15
Failed to complete all rabies vaccinations	Important feature of PEP. Should be known by Study Day 29	29

Failure to treat all exposure sites	Documented cause of treatment failure. Should be discovered early from wound state and investigation	15

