7.2 Demographics and Protocol Compliance

Demographic parameters (age, gender, and race/ethnicity) and other baseline characteristics will be summarized by treatment group for all subjects in the safety population.

Subject enrollment to each study group will be conducted based on timing of completion of study eligibility requirements. Randomization will be adjusted by the randomization center to maintain stratification and site allocation. Any resulting imbalance in baseline characteristics between study groups will be examined.

Listings of randomized subjects who missed any dose of Study Drug or rabies vaccine and of subjects with protocol deviations (to be defined in the statistical analysis plan) will be provided.

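### Protocol 3.2.8 lets per-protocol exclusions, some of which arise after treatment, feed back into later randomisation

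*Protocol*

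**What the plan says.** - **Protocol 3.2.8.** The Board may remove randomised subjects from the per-protocol population. One recipient of its decisions, besides the DSMB, is "the study enrollment center for the adjustment of randomization to maintain stratification and distribution of cases at the different sites". On blinding: "The Per-protocol Adjudication Board will review blinded data and will not be able to unblind subjects or data". Excluded subjects stay in the as-treated population, and the sponsor keeps a roster of exclusions with reasons.
- **Protocol 2.6.2.** "Within NRG enrollment subjects with head or neck bites or bites to genitalia will be stratified on a 1:1 basis into SYN023 or HRIG treatment", so the balance is between arms. Protocol 2.3 and SAP 4.1 add that the randomisation center will adjust randomisation so that these wounds are split about equally between the treatment groups.
- **Protocol 2.7.** "Subjects will not be replaced after randomization". Protocol 2.3 and SAP 4.2 say the same.
- **Protocol 2.8**, repeated in SAP 4.2. "Allocation of randomization among sites will be adjusted to accommodate stratification of head, neck or genitalia bites or site enrollment imbalances". Protocol 7.2 is similar: "Randomization will be adjusted by the randomization center to maintain stratification and site allocation". Neither names per-protocol status as a trigger.
- **Protocol 3.2.6.** The exclusion reasons include "Failed to complete the scheduled rabies vaccinations through Study Day 29", prohibited treatment during the trial, newly developed HIV infection and a second exposure requiring prophylaxis. They also include facts fixed before dosing, such as Study Day 1 RVNA, animal species and the 54-hour limit. The list is open-ended.
- **Protocol 3.3.** A statistician outside the analysis prepares the schedule. The randomisation procedure itself was not yet available.

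**The concern.** Stratified randomisation balances the arms on baseline factors among everyone randomised. It needs no correction when a subject later leaves an analysis set. If an exclusion disturbs the 1:1 balance of the bite stratum and the center restores it, the next assignments must favour the arm that lost the subject. Treatment assignment then depends on what happened to earlier subjects after they were treated.

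This alone does not bias a comparison if new subjects are exchangeable over time. The risk comes from combining it with other features of the plan. No rule is written, so whether and how to adjust is left to the center. The allocation ratio could drift during enrolment, while the primary tests in SAP 8.1.1 are plain ratios with no stated adjustment for stratum, site or time. The primary analysis uses the per-protocol population, the same set whose exclusions would drive the adjustment. An assessor could not reconstruct the allocation process from the documents.

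**Working it through.** **1. Does the clause reach treatment arms, or only sites?** Section 3.2.8 gives two aims: maintaining stratification, and distributing cases across sites. Sections 2.6.2 and 2.3 define the stratification as balance between SYN023 and HRIG. If adjustment used only baseline counts of all randomised subjects, exclusions would not need to be sent for this purpose. The natural reading is that exclusions change the counts that later assignment seeks to balance.

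**2. Can exclusions arrive while subjects are still being assigned?** Protocol Table 3.2.6-1 gives likely discovery at about day 15 (untreated exposure sites, wrong animal, late start), day 29 (incomplete vaccination), day 43 (Day 1 RVNA, wrong drug or dose) and up to day 365 (prohibited treatment, HIV, second exposure). SAP 4.3 has the Board decide before each DSMB meeting. Protocol 5.1.5.4 places an NRG safety review after 80 subjects complete Study Day 99, while enrolment continues. So some exclusions can arrive in time and later ones cannot.

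**3. The plan's own allowance.** Inputs are in Protocol 7.8.4: ratio 1.45, margin 1.10, CV 108.78%, one-sided alpha 0.025, power 80%.
- SD on the log scale = √ln(1 + 1.0878²) = 0.8837.
- n per arm = 2 × (1.960 + 0.842)² × 0.8837² / [ln(1.45/1.10)]² ≈ 161, or 322 in total, against 320 stated.
- 320 × 1.15 = 368, as stated. Expected losses are already built into enrolment.

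**4. Size of the effect if exclusions are fed back.** The documents give no algorithm and no exclusion rates by arm, so both are assumed here. Let a and b be the proportions retained on SYN023 and HRIG, with N = 368. Full rebalancing on retained subjects randomises N × b/(a + b) to SYN023.

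| Assumed exclusion, SYN023 v HRIG | Schedule | Randomised | Per-protocol | Excluded |
|---|---|---|---|---|
| 16% v 10% | Fixed | 184 / 184 | 154.6 / 165.6 | 29.4 / 18.4 |
| 16% v 10% | Full feedback | 190.3 / 177.7 | 159.9 / 159.9 | 30.5 / 17.8 |
| 20% v 10% | Fixed | 184 / 184 | 147.2 / 165.6 | 36.8 / 18.4 |
| 20% v 10% | Full feedback | 194.8 / 173.2 | 155.9 / 155.9 | 39.0 / 17.3 |

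The shift is 190.3 − 184 = 6.3 subjects (1.7% of 368) in the first case and 10.8 (2.9%) in the second. These are ceilings, because they rebalance the whole NRG at once. For a stratum of m subjects the shift is m × (0.90/1.74 − 0.5) = 0.017m, or m × (0.90/1.70 − 0.5) = 0.029m. The documents do not give m for head, neck and genital bites.

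A simulation of 2,000 trials at 20% v 10% assigned each subject to the arm with fewer retained. With exclusions known 15, 43 or 150 enrolments later, randomised numbers averaged 194/174, 194/175 and 190/178 (rounded). With 15% in both arms the mean stayed at 184/184.

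**5. Do exclusions stay visible?** Yes. Randomised minus per-protocol gives about 30 v 18 with feedback and 29 v 18 without (first case). In the simulation at 20% v 10%, the chance that a 5% chi-square test detects the difference was 77% to 79% with or without feedback.

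**6. Does feedback gain precision?** The variance of the difference in log means is proportional to the sum of reciprocal arm sizes. Fixed: 1/154.6 + 1/165.6 = 0.0125. Feedback: 2/159.9 = 0.0125. The two are algebraically equal, since both reduce to 2(a + b)/(N·a·b). With equal variances, rebalancing gains nothing.

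**The case against.** The strongest reply is that the clause is administrative. Section 2.8 and SAP 4.2 speak of allocation among sites. The Board is blinded, many exclusion reasons are baseline facts, an independent statistician prepares the schedule, and no text says that schedule is overridden. This supports treating the effect as small and the intent as unclear. It does not remove the problem: 3.2.8 names adjustment of randomisation as the purpose of forwarding exclusions, and 2.3 ties such adjustment to the treatment groups. Blinding the Board limits selective exclusion, but not what the center does with an exclusion.

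Four stronger readings are tempting but not supported:

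- **That the feedback hides differential exclusion.** Equal per-protocol totals could mislead only someone who read nothing else. The SAP 5.1 disposition table, the SAP 5.2 deviation table, grouping by treatment where applicable (SAP 4), the sponsor's roster and the as-treated analysis of all four elements (SAP 8.1.2) keep it visible.
- **That it is replacement in breach of 2.7.** Enrolment is fixed at 368, nobody is added, and excluded subjects remain in the as-treated population. It is at most compensatory refilling of a place in an arm.
- **That 48/368 = 13% of assignments could be compensating.** The 48 includes loss to follow-up, which under Protocol 3.12.6 can be declared only at the calculated Day 365 visit date, and exclusions found too late to compensate.
- **That sites could predict the next assignment.** The documents send exclusions to the DSMB and the enrollment center, not to sites, and the Board's decisions appear to be batched.

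**Conclusion.** The point holds as a defect in the allocation rule. Section 3.2.8, read with 2.6.2 and 2.3, allows later treatment assignment to depend on exclusions that can arise after treatment. It uses a trigger that 2.8 does not list and sits badly with the non-replacement rule. The documents do not show that this would happen often or materially bias the result. Under assumed rates of 16% v 10% or 20% v 10%, about 6 to 11 of 368 subjects would change arm if the whole NRG were rebalanced, and fewer if only the bite stratum were. A net shift between arms needs exclusion rates that differ by arm and exclusions found while enrolment continues. With equal rates the average allocation is unchanged, though individual assignments would still depend on earlier exclusions. The clause is worth removing because it gives up a fixed, reconstructable allocation for no gain in precision.

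**What to change.** - In Protocol 3.2.8, delete the forwarding of exclusions to the enrollment center for adjustment of randomisation. Keep the report to the DSMB and the sponsor's roster.
- In Protocol 2.3, 2.8 and 7.2, the matching Study Abstract text, and SAP 4.1 and 4.2, state that any adjustment uses only baseline bite stratum and site counts of all randomised subjects, whatever their later per-protocol status. State also that treatment assignment does not change in response to exclusions.

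The allocation method within that rule is the sponsor's choice. Reporting exclusions by arm is largely planned already; one sentence in SAP 5.1 or 5.2 would make it explicit.

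The cost is wording. Per-protocol arm sizes may differ by a few subjects (for example 155 v 166 at 16% v 10%), with no loss of precision compared with rebalancing when the arms have equal variance.

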3.3 Study Randomization

Subjects will be randomized to the study by and IVRS/IWRS. The procedure for randomization will require CRO contract before completion. Since a CRO has not been contracted this information is not yet available for this version.

The randomization schedule will be prepared by a statistician who will not be involved in the analysis of the study in order to maintain the blind of the study team. A subject is considered randomized when a subject identification number has been assigned to them on Study Day 1.

3.4 Blinding

3.4.1 Blinding at the Study Level

The LRG and the NRG are both blinded until Study Day 365. If the last subject in LRG reaches Study Day 365 even if the NRG is still in progress, then the LRG group may be unblinded. The LRG may be unblinded to the extent recommended or required by the DSMB for analysis of safety or efficacy data for Study Day 99 DSMB review. The NRG group will remain blinded until Study Day 365. The DSMB will conduct unblinded analyses before Study day 365 as specified by the protocol and inform the sponsor of the overall results of those analyses. The purpose of these analyses is to permit advancement of the study risk groups and to inform the sponsor so that product development decisions can be made. Since investigational agent will have been administered to the NRG, blinded specimens for analysis collected and individual treatment assignments still unknown to the sponsor for the NRG, this should not affect the conduct of the trial during the observation period required for clinical rabies surveillance.

The NRG is powered for the efficacy outcomes of the study. The smaller LRG's purpose is primarily pharmacodynamic and pharmacokinetic. The LRG will remain blinded for safety and clinical efficacy through Study Day 365. The sponsor will know without blinding that there are no rabies cases but the rabies risk in the LRG is much lower than from the NRG so the clinical efficacy results from the LRG do not mean the same thing. The DSMB must give permission for advancement to the NRG. The combined LRG and NRG study will take years to complete without information for Synermore. The sponsor will be able to infer meager pharmacodynamic characteristics from the progress of the blinded study. The LRG pharmacodynamic and pharmacokinetic data will help in planning and maintaining support for SYN023 development. Once this cohort has final data there is no reason to continue to blind the LRG study cohort since its efficacy results are objective, separately analyzed and cannot affect the efficacy conclusions from the NRG.

3.4.2 Blinding at the Site Level

The site's investigational pharmacist or product manager (or designee) will need to be unblinded in order to manage Study Drug inventory and prepare doses. Other unblinded persons on the study are the unblinded study monitor that will need to audit Study Drug stocks and the study monitor(s). All unblinded persons must take care to not reveal individual subject treatment regimen assignments to any other member of the study team.

The investigational pharmacist or product manager must be a designated study team member who is not an employee of the sponsor and who will have no other clinical or regulatory

responsibilities associated with the conduct of the study during the entire study period. Unblinded study personnel must not participate in the evaluation of adverse events. A Delegation of Authority Log will be maintained by the site and will identify the individual(s) authorized to function as the Study Drug manager, i.e., individuals with access to study blinding information.

Labels accompanying the syringes of prepared Study Drug will not indicate which Study Drug is in the syringe but will only contain the study identification and subject ID number. Identical syringes and needles will be used for preparation and administration of each Study Drug.

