Exposure from animal not in inclusion criteria	Some not animals don't transmit rabies. Should be discovered early from wound state and investigation	15
Serum RVNA \geq 0.1 IU at Study Day 1	Indicates previous Rabies vaccination. Results from central reference laboratory needs shipment, processing and return of results	43
Receives prohibited treatment during the trial	Has potential to increase or decrease vaccine protection. Will turn up in monitoring visit	365
Are found not to have a modified WHO Category 3 exposure (Table 2.2-1, Section 3.9.4)	Different rabies risks. Should turn up in local investigation or monitoring	15
Second high risk animal bite or contact requiring PEP	Subjects should have same rabies risk. Should turn up in monitoring.	365

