8 DATA COLLECTION, MONITORING, AND RECORD RETENTION

For the purpose of monitoring and auditing the study, source documentation will consist of existing medical records and/or study records developed and maintained by the investigator. Any source document templates provided by the sponsor or its designee will serve as supplements to the subject's study record.

Data recorded on source documents will be transcribed onto case report forms (CRFs) provided by the sponsor or entered using electronic case report forms (eCRFs) using an Electronic Data Capture (EDC) system provided and approved by the sponsor. Completed, original CRFs will be retrieved by the sponsor or its designee and a copy of each completed CRF will be retained at the clinical site as part of the study records.

The study will be monitored regularly by the sponsor or its designee throughout the study period. For studies of unapproved investigational products, all study records (source documents, signed informed consent forms, copies of CRFs, IRB/IEC correspondence and approval letters, Study Drug management records) will be kept secured for a minimum of 2 years following the marketing of the investigational product or for 2 years after the discontinuation of the IND (or CTA, etc.). The investigator will ensure that study records are not disposed of or removed from the clinical site without prior notification and approval from the sponsor or its designee.

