4.2.3. Blinding and Unblinding

The LRG and the NRG are both blinded until Study Day 365. If the last subject in LRG reaches Study Day 365 even if the NRG is still in progress, then the LRG group may be unblinded. The NRG group will remain blinded until Study Day 365. The DSMB will conduct unblinded analyses before Study Day 365 as specified by the protocol and inform the sponsor of the overall results of those analyses. The purpose of these analyses is to permit advancement of the study and to inform the sponsor of the status of certain endpoint elements so that the sponsor may

make product development decisions. Since investigational agent will have been delivered, still blinded specimens for analysis collected and individual treatment assignments still unknown to the sponsor, this should not affect the conduct of the trial during the observation period required for clinical rabies surveillance.

The site's investigational pharmacist or product manager (or designee) will need to be unblinded in order to manage study drug inventory and prepare doses. Other unblinded persons on the study are the unblinded study monitor that will need to audit study drug stocks and the study monitor(s). All unblinded persons must take care to not reveal individual subject treatment regimen assignments to any other member of the study team.

The investigational pharmacist or product manager must be a designated study team member who is not an employee of the sponsor and who will have no other clinical or regulatory responsibilities associated with the conduct of the study during the entire study period. Unblinded study personnel must not participate in the evaluation of AEs. A Delegation of Authority Log will be maintained by the site and will identify the individual(s) authorized to function as the study drug manager, i.e., individuals with access to study blinding information.

Labels accompanying the syringes of prepared study drug will not indicate which study drug is in the syringe but will only contain the study identification and subject ID number. Identical syringes and needles will be used for preparation and administration of each study drug.

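### As written, Protocol 3.4.2 and SAP 4.2.3 unblind the routine study monitors, who are a named route for finding three kinds of per-protocol exclusion

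*Protocol*

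**What the plan says.** Protocol 3.4.2 names the site's investigational pharmacist or product manager as unblinded and then adds: "Other unblinded persons on the study are the unblinded study monitor that will need to audit Study Drug stocks and the study monitor(s"). SAP 4.2.3 carries the clause over unchanged, again listing "the unblinded study monitor that will need to audit study drug stocks and the study monitor(s"). Both sections tell unblinded persons not to disclose assignments and keep them out of adverse event evaluation. Neither restricts their part in finding or reporting protocol deviations.

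On who monitors, Protocol 8 says: "The study will be monitored regularly by the sponsor or its designee throughout the study period".

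Protocol 3.2.6 lists the deviations that remove a subject from the per-protocol population. Table 3.2.6-1 gives the likely time at which each comes to light, "based on the occurrence of site review, monitoring visits and vaccination schedules". For prohibited treatment the entry reads "Will turn up in monitoring visit". For an exposure that is not modified Category 3 it reads "Should turn up in local investigation or monitoring". The row for a second exposure also names monitoring.

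The per-protocol population is primary (SAP 4.3), and the primary efficacy analyses use it for the NRG (SAP 8.1). The Per-protocol Adjudication Board decides exclusions on blinded data (Protocol 3.2.8).

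**The concern.** A separate unblinded monitor is normally appointed so that the monitors who read clinical source records can stay blinded. The clause in 3.4.2 undoes that separation. The monitors who would come across a prohibited medication or a further exposure would then know the subject's arm.

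What is at stake is membership of the primary population. The RVNA result comes from a laboratory and a monitor cannot move it. A monitor can affect how hard records are searched and which findings are referred. If that differs by arm, exclusions differ by arm, and the Day 8 and Day 99 comparisons are made on sets selected after randomization with knowledge of treatment. A board that sees blinded data can judge the cases put before it fairly, but it cannot restore cases that were never raised.

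**Working it through.** The plan gives no figure on this point, so there is nothing to recompute. The check sets the sections side by side.

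1. **Who is unblinded.** Protocol 3.4.2 and SAP 4.2.3 list the pharmacist or product manager, the drug-stock monitor, and the study monitor(s). The local medical monitor is blinded (Protocol 5.1.3), but that is a different role. No section of either document says that routine clinical monitors are blinded.

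2. **Can the sentence be read otherwise?** One could take the unblinded monitor as auditing both the drug stocks and the study monitors. That is strained. The natural reading lists two kinds of unblinded monitor.

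3. **Consistency with other sections.** Protocol 3.4.1 and SAP 4.2.3 defend early DSMB reporting partly on the ground that the sponsor does not know individual assignments. Under Protocol 8 the sponsor or its designee does the monitoring. Unblinded routine monitors fit badly with that premise.

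4. **Route into the primary population.** Table 3.2.6-1 has 12 rows, and 3 name monitoring:

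| Deviation | Detection route named | Likely day of discovery |
|---|---|---|
| Prohibited treatment | Monitoring visit | 365 |
| Exposure not modified Category 3 | Local investigation or monitoring | 15 |
| Second exposure needing prophylaxis | Monitoring | 365 |

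   Two of the three can therefore surface after the Day 99 sample. The deviation list is not exhaustive (Protocol 3.2.6), and the Board can add to it while the study runs (SAP 5.2).

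5. **What each safeguard covers.**
   - The blinded Board (Protocol 3.2.8) covers the decision to exclude, not the search or referral.
   - The blinded data review meeting and the finalizing of analysis sets before unblinding (SAP 4.3, 5.2) cover late changes to the sets, not what was looked for earlier.
   - The duty not to disclose covers passing the assignment on, not acting on it.
   - The bar on unblinded staff covers adverse event evaluation only.
   - The as-treated analysis of all four primary elements (SAP 8.1.2) is untouched by per-protocol exclusions and would help to show a result driven by them. SAP 8 makes it supportive, so it does not decide the primary result.

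6. **Direction.** Prohibited medication includes rabies vaccine and immunoglobulin, which would tend to raise RVNA, and early immunosuppressants, which would tend to lower it (Protocol 3.12.4). A second course of prophylaxis would tend to raise it. For an exposure that is not Category 3, the table's reason for exclusion is a different rabies risk, with no stated link to RVNA. No single direction follows.

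**The case against.** The strongest reply is that this is a slip of the pen. Naming one monitor as the unblinded one makes little sense unless the others are blinded, and the sponsor's stated ignorance of assignments points the same way. That is probably right about intent. It does not change what both documents tell the people who run the study.

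The second reply is that monitoring is only one route. A reader might infer that the Board's cases come only from people who know the arm. The documents do not support that. Sites record every deviation as it occurs (Protocol 3.12.5), collect prohibited medications through Day 365 (3.12.4), take an interval history at each visit after Day 1, and record exposure facts from confirmation visits on Days 4 and 8 (Appendix D). Day 1 RVNA, HIV status and vaccination completion are laboratory or record facts. The Board itself reviews screening and management information. This reply stands and confines the point to the three rows above.

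The sponsor also argues, in its rationale for blinding, that objective endpoint elements make blinding weaknesses secondary. That holds for the RVNA measurement. It does not extend to who stays in the analysis set.

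A reader might further infer that the blind is broken at randomization, because Protocol 2.6.2 has the center "return the randomization assignment in written communication to the study site". The documents do not bear this out. The unblinded pharmacist is a member of the site, syringe labels do not identify the drug (3.4.2), and an investigator must ask the pharmacist in writing for an emergency unblinding (3.4.3). The plan therefore presupposes that the pharmacist holds the assignment. Protocol 3.3 also says that the randomization procedure was not yet complete.

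**Conclusion.** The point holds in a limited form. As written, both documents unblind the routine monitors, and no rule stops them from finding or referring per-protocol deviations. Arm-dependent detection or referral is therefore possible for three exclusions that feed the primary population. The existing safeguards reduce the risk but do not remove it. No actual bias is shown.

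No size can be given. A reader might try to put a percentage shift on the Day 99 ratio by supposing that excluded subjects have lower RVNA than the rest. The documents give no RVNA values for such subjects, and for rabies vaccine, immunoglobulin or repeat prophylaxis the expected effect runs the other way. Nor does the planned allowance of 48 NRG subjects (48/320 = 15%) measure the scope for such bias: it covers loss to follow-up and all exclusions in both arms.

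The conclusion assumes that the sentence means what it says. If routine monitors are blinded in practice, the defect is one of text only, but the text still needs correcting because it is the only statement of their status.

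**What to change.** - In Protocol 3.4.2 and SAP 4.2.3, delete the words that add the study monitor(s) to the unblinded list, and state that routine clinical monitors are blinded.
- Limit the unblinded drug-stock monitor to drug accountability. That monitor should refer only wrong-drug and wrong-dose deviations to the Board, in a form that does not reveal the arm.
- Optional clarification: in Protocol 2.6.2 and SAP 4.2.2, name the unblinded pharmacist as the recipient of the written assignment.

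The cost is wording in two documents. The separate drug-stock monitor and the unblinded pharmacist are already planned, and the design, sample size and analyses do not change.
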